6.1. Primary Study Endpoints

The primary endpoint for the study is:

- IOI-HA Clinic Visit 3 scores. The average total IOI-HA scores will be compared between the Self-Fit Group and Pro-Fit Group

The International Outcome Inventory for Hearing Aids (IOI-HA) is a seven-item validated questionnaire designed to be generally applicable in evaluating the effectiveness of hearing aid treatments. The inventory was developed to facilitate cooperation among researchers and program evaluators in diverse settings. The survey has seven items assessing (1) daily hearing-aid use, (2) benefit, (3) residual activity limitation, (4) satisfaction, (5) residual participant restriction, (6) impact (of hearing impairment) on others, and (7) quality of life. Each of the 7 items are scored on a 1 (poorest) – 5 (best) Likert scale and summed to obtain a total outcome score ranging from 5 to 35 where higher scores are better.

6.2. Secondary Endpoints

There are no secondary endpoints in this study. Additional descriptive analyses will include the following:

- Comparison of Speech in Noise (SIN) scores between Self-Fit Group and Pro-Fit Group
- Comparison of Real Ear Measures (REM) between Self-Fit Group and Pro-Fit Group
- Summary of baseline pure tone audiometry (PTA) results
- Summary of baseline bone conduction audiometry results
- Summary of baseline tympanometry results

6.3. Study Hypotheses

The primary endpoint hypothesis for the clinical validation study is as follows:

$$H_0: \text{Mean}(\text{IOI-HA}_{\text{Pro-Fit}}) - \text{Mean}(\text{IOI-HA}_{\text{Self-Fit}}) > 3$$

$$H_1: \text{Mean}(\text{IOI-HA}_{\text{Pro-Fit}}) - \text{Mean}(\text{IOI-HA}_{\text{Self-Fit}}) \leq 3$$

where $\text{Mean}(\text{IOI-HA}_{\text{Pro-Fit}})$ and $\text{Mean}(\text{IOI-HA}_{\text{Self-Fit}})$ are the average follow-up (i.e., clinical visit 3) IOI-HA scores for the Pro-Fit and Self-Fit groups, respectively.

[figure not shown]
The non-inferiority margin of 3 points was determined based on the estimated variation from mean scores previously reported (i.e., mean IOI-HA of 25.5 - 28.9) and is justified because 3 points is within a reasonable margin of variation for the study instrument at the subject level.

7. Statistical Considerations

[figure not shown]
7.1. Sample Size

Preceding the start of the clinical validation study, approximately participants will be enrolled into a sub-study cohort. These participants will follow the same study procedures outlined in this protocol. After the completion of the sub-study, the clinical validation study

will commence. [REDACTED]

The approach to sample size determination of the clinical validation study is based on a two-sample independent t-test comparing group means assuming equal variances between groups. [REDACTED]

[REDACTED] a total of N=112 (56 per group) will be enrolled in the pivotal portion of the study. To summarize:

Clinical Validation Study: Approximately 112 participants will be enrolled

Sub-Study: Approximately [REDACTED] participants will be enrolled

7.2. Randomization and Blinding

Eligible subjects will be randomized (1:1) to either the Self-Fit or the Pro-Fit groups using a single pre-determined block randomization schedule with a fixed block size of 4. The randomization will not incorporate any pre-stratification. Subjects will not be blinded to their randomly assigned group.

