1.4. Study Design

A prospective, multi-center, non-significant risk study.

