1.13. Study Design

Prior to enrollment, all participants will have an examination of the ears by an audiologist using PTA reference testing to assess for any contraindications to proceeding. PTA will include the NAL-NL2 PF algorithm assessment [2]. Participants with >60 dB HL at 0.25-3kHz and >65 dB HL at 4kHz in either ear will not be invited to continue in the Clinical Validation Study. Following the enrollment process, participants will be randomized to the SF group or the PF group.

On *Clinic Visit 1*, enrolled participants will be provided with wireless headphones and a smartphone for use throughout the study. Those in the SF group will have software assisted self-tuning of their wireless headphones and may further fine-tune to preference. Those in the PF group will have settings selected by an audiologist who may further fine-tune as guided by participant interaction. Participants will leave clinic for *Home Interval 1* and return after 3-8 days of wearing the headphones in their routine environment to guide fine-tuning settings by self or audiologist on *Clinic Visit 2*. This second clinic visit will additionally include Real Ear measures with headphones *in situ*, and unaided baseline SIN testing. Participants will leave for *Home Interval 2* for 14-22 days of continued headphone use in their routine environment and will be advised to adjust settings with their software based on preference. Upon returning for final visit on *Clinic Visit 3*, participants will complete the IOI-HA survey, have final Real Ear measures with headphones *in situ*, and complete aided SIN testing with their tuned headphones *in situ*. Finally, participants will return all devices and offboard from the study.

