9.5. Randomization and Blinding

Eligible subjects will be randomized (1:1) to either the Self-Fit or the Pro-Fit groups using a single pre-determined block randomization schedule. The randomization will not incorporate any pre-stratification. Subjects will not be blinded to their randomly assigned group.

Additional details of the randomization schedule (e.g., block size, etc.) may be found in the study Statistical Analysis Plan (SAP).

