After a particular hearing loss recruitment category has been filled, subjects identified at screening within that category may be dispositioned prior to randomization. Information collected at the screening visit and clinic visit 1 (e.g., informed consent, medical history, demographics, otoscopy exam, perceived hearing loss questionnaire, eligibility criteria, and pure tone audiometry, tympanometry, and bone conduction) for these subjects will be presented in the listings but will not be included in any of the full analysis set analyses because they were not randomized.

5. Study Procedures

Participants will have a screening visit and up to three scheduled clinic visits interspersed by two home intervals. The participants enrolled into the sub-study cohort will follow similar study procedures:

- Screening Visit (~2 hours): informed consent, potential Pure Tone Audiometry (air conduction audiometry), medical history, and brief physical exam of the ears conducted by site clinician; time from Screening Visit to Clinical Visit 1 will be no longer than 3 weeks

[figure not shown]

- Clinic Visit 1 (~1.5 hour): examination of the ears by an audiologist who may remove ear wax if deemed required and consented to by participants, bone conduction audiometry, tympanometry, Pure Tone Audiometry (air conduction audiometry), enrollment, and baseline hearing assist software settings
- Home Interval 1 (3-8 days; begins on same day as Clinic Visit 1): at-home observations of baseline hearing assist software settings during participant's daily activities. Participants have the option to make setting adjustments during this interval for listening needs and/or to avoid discomfort, regular charging of study devices, and encouraged daily use of devices. Participants who have no evidence of at least daily use for several days will be contacted by study staff to assess for troubleshooting needs. Minimum expected wear time is at least 30 minutes per day for at least 3 days during this interval.
- Clinic Visit 2 (~1.5 hours): examination of the ears by an audiologist who may remove ear wax if deemed required and consented to by participants, hearing assist software setting fine-tuning, Real Ear measures, and SIN objective hearing test

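### A fixed block size of 4 on one open-label schedule makes some allocations more predictable than they need be; varying the block sizes is a cheap, minor improvement

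*SAP*

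**What the plan says.** SAP 7.2 states that "Eligible subjects will be randomized (1:1) to either the Self-Fit or the Pro-Fit groups" from a "single pre-determined block randomization schedule with a fixed block size of 4". It adds that "The randomization will not incorporate any pre-stratification" and that "Subjects will not be blinded to their randomly assigned group". Protocol 9.5 describes the same design but leaves the block size to the SAP.

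Staff learn the arm too, at least at the fitting visit: "Those in the PF group will have settings selected by an audiologist" (Protocol 1.13). Protocol 1.4 describes the trial as "A prospective, multi-center, non-significant risk study". The number of sites is not given.

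Three decisions before randomisation leave room for judgement:

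- Once a hearing-loss category is full, "subjects identified at screening within that category may be dispositioned prior to randomization" (SAP 4). The rule is permissive, and the text does not say who applies it.
- One exclusion in Protocol 4.4 rests on the investigator's opinion about adherence.
- Another exclusion in Protocol 4.4 rests on the audiologist's judgement of acoustic stability.

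Randomisation follows enrolment (Protocol 4.7). The supplied text does not say who holds the schedule, how an assignment is released, or who can see earlier assignments.

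**The concern.** In a permuted block of fixed, known size, the last places are determined by the earlier ones. Where assignments are open, anyone who follows the sequence can count down to a known allocation. If that person can also influence whether the next candidate is randomised, the arms may come to differ in the kind of person entered. Random allocation then no longer guarantees comparability.

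This matters more here than in a blinded trial with an objective outcome. The primary endpoint is the self-reported IOI-HA total from unblinded participants, tested against a margin of 3 points (SAP 6.1 and 6.3). A distortion could run in either direction, towards or away from non-inferiority. Nor does the primary model adjust for prognostic factors as a matter of course: SAP 9.5 admits a baseline factor only if it is related to missingness at p < 0.15.

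**Working it through.** The documents state no predictability figure, so there is none to reproduce. The inputs are block size 4, allocation 1:1 and no stratification (SAP 7.2), and N = 112 (SAP 7.1). That gives 112/4 = 28 full blocks and exactly 56 per arm.

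**1. Full visibility, fixed blocks of 4.** There are 6 equally likely blocks with two places per arm. AABB and BBAA determine the last two places; the other four determine only the last.

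- Certain allocations per block: (2×2 + 4×1)/6 = 1.333. As a share, 1.333/4 = 33.3%, or 112 × 0.333 ≈ 37 allocations.
- Best guess (the arm with more places left) by position in the block: 1/2, 2/3, 2/3, 1. The average is 2.833/4 = 70.8%.

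**2. A site that sees only its own assignments but knows list positions.** Let s be its share of enrolment, with arrivals at random. It is certain at the third place if both earlier places were its own and in the same arm: s²/3. It is certain at the fourth if the two matching earlier places were both its own: s². Averaged over four places, (s²/3 + s²)/4 = s²/3.

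- s = 0.5: 0.25/3 = 8.3%
- s = 0.8: 0.64/3 = 21.3%

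**3. A site that sees only its own assignments and not positions.** It can only guess the arm it has used less. Simulated accuracy over 112 allocations:

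| Share of enrolment | Fixed 4 | Mixed 4/6/8 |
|---|---|---|
| 25% | about 52% | about 52% |
| 50% | about 53% | about 53% |
| 70% | 54.7% | 54.8% |
| 80% | 56.1% | 55.9% |
| 90% | 58.6% | 58.1% |

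Varying the blocks makes almost no difference here.

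**4. Randomly varying blocks, full visibility.** The observer knows the set of sizes but not their order (simulated, N = 112).

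| Scheme | Certain | Best guess | Mean end imbalance | Largest |
|---|---|---|---|---|
| Fixed 4 | 33.3% | 70.8% | 0 | 0 |
| 4 and 6 | 5.4% | 69.2% | 0.5 | 2 |
| 4, 6 and 8 | 2.3% | 67.9% | 0.6 | 4 |

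**5. What this could mean in IOI-HA points.** The documents give no figure for how far selection might shift prognosis. Assume d = 1 point, up for one arm and down for the other.

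- *Acting only on certain allocations, full visibility:* bias = 2 × certain share × d. Fixed 4: 2 × 0.333 = 0.67. Mixed 4/6: 2 × 0.054 = 0.11. Mixed 4/6/8: 2 × 0.023 = 0.05.
- *Acting on every best guess, full visibility:* bias = 2d(2p − 1), where p is the accuracy. Fixed 4: 2 × (2 × 0.708 − 1) = 0.83. Mixed 4/6/8: 2 × (2 × 0.679 − 1) = 0.72.
- *One site with an 80% share and known positions, acting on its certain allocations:* 2 × 0.8 × 0.213 = 0.34 study-wide under fixed 4.

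All of these scale with d. For d from 0.5 to 2, the 0.67 becomes 0.33 to 1.33, against a margin of 3.

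**6. Price of a final imbalance of 4.** A 58/54 split multiplies the standard error by √[(1/58 + 1/54)/(2/56)] = 1.0006.

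**The case against.** The case against acting is substantial.

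- *Knowledge of the block size.* The protocol omits it. A reader might infer that because the size stands in the SAP, recruiters knew it. The documents do not say that site staff had the SAP during enrolment. A fixed size of 4 can be inferred from an observed sequence, but only by someone who sees enough of it.
- *Who sees and who decides.* The adherence and acoustic-stability judgements are made by the investigator and the audiologist. On a shared list they are close to chance unless they can place themselves in the sequence. A reader might assign the 33% to central or contract-research staff, but nothing gives those staff an eligibility decision. Anyone holding the schedule itself knows every allocation whatever the block size.
- *A dominant site.* It is tempting to say that varying blocks mainly protects against one large site. Without list positions, step 3 shows no material gain even at a 90% share. The concern about a large site depends on its inferring positions, and the documents do not say that positions are visible.
- *Size of the gain.* The fall in certain allocations looks dramatic; the fall in best-guess accuracy is 2 to 3 percentage points.
- *Existing safeguards.* An enrolled subject has by definition met all criteria (Protocol 4.10). Eligible people who were not randomised stay in the Eligible Analysis Set (SAP 8), and their screening data are listed (SAP 4). Accountability and demographics are tabulated by site (SAP 13). Selective turn-away is therefore partly auditable.
- *Adjustment.* A reader might infer that no adjustment could repair selection. That is too strong: selection on recorded factors such as age or four-tone average could be adjusted for, although the planned model does not do so routinely. Selection on unrecorded factors could not.

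Most of this stands, and it reduces the exposure. It does not remove the case for a change that costs almost nothing before enrolment starts. Entry remains partly discretionary, and no concealment procedure is described.

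**Conclusion.** The point holds as a minor one. A fixed block of 4 gives a fully informed observer certainty about 33% of allocations. It gives a site that can infer list positions certainty about 8% (50% share) to 21% (80% share) of its own. A site without positions gains little: about 52% to 59% under either scheme.

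These figures assume that the block size is known or inferred and, for the site figures, that arrivals are random. The 33% also requires sight of every earlier assignment. The number of sites and the visibility of assignments are not stated. A concealment procedure may exist in a document not supplied, and nothing here is evidence that selection would occur. The bias figures in points rest on an assumed shift and are illustrations only.

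This is a cheap improvement, not a flaw that threatens the primary conclusion.

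**What to change.** In SAP 7.2, before the first participant is randomised:

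1. Replace the fixed block of 4 with randomly varying block sizes, for example 4 and 6, or 4, 6 and 8.
2. Move the sizes to a randomisation file with restricted access, and say only that they vary.
3. State who holds the schedule, and that each assignment is released only after the eligibility decision and any category-closure decision have been recorded.

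The third item matters most for a site without list positions, because varying the blocks does little there. If such a procedure already exists, stating it is enough for that item.

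The cost is one regenerated schedule and a few lines of SAP text. The arms may end unequal by up to 2 participants (4/6) or 4 (4/6/8), with a mean of about 0.6 or less. The effect on precision is negligible. Sample size, endpoint and visits do not change.

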7.3. Significance Level

The primary hypothesis test will use a one-sided significance level of 0.025. Analyses of the exploratory objectives will use 95% confidence intervals. Multiple comparison corrections will not be used.

7.4. Missing Data

Rigorous efforts will be made to ensure all subjects are compliant with the protocol. However, some subjects may drop out prematurely or some planned measurements may not be analyzable due to missing data. The handling of missing data for the primary endpoint analyses is described in Section 9.5. Exploratory efficacy analyses will be performed on available data. For subjects with one unanswered question on the IOI-HA, the mean of the other six questions will be calculated to replace the missing data; otherwise, the IOI-HA survey score will be considered missing.

7.5. Subgroup Analyses

There are no planned subgroup analyses.

7.6. Interim Analyses

There are no interim analyses planned in this study.

8. Analysis Sets

The following analysis sets are defined for this study.

Eligible Analysis Set: All subjects who sign informed consent and meet eligibility criteria for the CV portion of the study. Some of these subjects may not have been randomized if the hearing loss recruitment category is already filled.

Full Analysis Set (FAS): All subjects who sign informed consent, meet eligibility criteria, and are enrolled and randomized into the CV portion of the study. This analysis set will be used for the primary endpoint analysis and to summarize subject accountability, protocol deviations, demographic and baseline characteristics, and adverse event data. Subjects in this analysis set will be analyzed “as randomized”.

Per Protocol Analysis Set (PPS): All subjects who meet predetermined minimum data usability criteria, and who do not have any major protocol deviations that would necessitate exclusion from analysis. Subjects in this analysis set will be analyzed “as treated”. This analysis set will be used as a supportive analysis of the primary endpoint. Subjects in the PP analysis set must meet the following two minimum usability criteria:

- 1) >10 minutes of Airpod wear for at least 1 day during home interval 1 AND
- 2) >10 minutes/day of Airpod wear for at least 7 days during home interval 2

The minimum wear times are justified to obtain the most accurate assessment of hearing aid benefit as measured by the IOI-HA questionnaire.

Complete Cases Analysis Set (CCAS): All subjects who have complete data for the efficacy endpoints of IOI-HA, QuickSIN, or Real Ear Measures. This analysis set will be used as a supportive analysis of the primary endpoint.

9. Analysis Approach

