4.7. Participant Enrollment

Before any study specific procedures are performed, informed consent will be obtained from each potential study participant:

Each participant who is screened for the research study will be assigned a unique participant identifier.

Randomization:

- Following the enrollment process, participants will be randomized into either SF or PF groups, so that approximately half of the useable datasets will derive from each group.

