4.8. Participant Discontinuation

A participant may voluntarily withdraw from the study for any reason, at any time. A participant may be discontinued from the study in any of the following circumstances:

- Any adverse event (AE) that renders the participant ineligible or in the opinion of the principal investigator (PI), makes it not in the best interest of the participant to continue participation.
- After enrollment, if a participant does not meet the inclusion/exclusion criteria of the study (either newly developed or not previously recognized).
- Protocol violation that renders data to be unusable or of questionable accuracy, in accordance with the Data Management and Quality Plan.
- Lost-to-follow up; unable to contact participant.
- Termination of the study by the PI or Sponsor.
- Withdrawal of consent: a research participant may withdraw from participation for any reason at any time.
- Loss of two study-provided devices (smartphone and/or wireless headphone(s) or case).
- PI discretion.

A participant who develops active ear disease (e.g., otitis media; otitis externa; acute tinnitus), even if unilateral, may be withdrawn per PI discretion from participation.

If a participant reports loud environmental sound exposure (e.g., concert; construction site; fireworks) during participation, this should be recorded as it may contextualize setting changes by the participant.

The PI or designee(s) will advise the discontinuation of any participant. Participants who discontinue or are discontinued should be compensated for the study visits they have completed, according to the compensation information in the Informed Consent Form (ICF).

In the event of a participant withdrawal, coded participant data that was previously recorded may be retained and used in accordance with the protocol and ICF. Participants who withdraw from the study must return certain study equipment and materials.

The reason for participant withdrawal from the study will be documented in the relevant tracking database(s). The PI or designee(s) will inform the participant of the reason for withdrawal, as well as recommend steps for seeking additional care from their physician, when applicable.

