9.3. Participant Population for Analysis

Full Analysis Set: All subjects who sign informed consent, meet eligibility criteria, and are enrolled and randomized into the study. This analysis set will be used for the primary endpoint analysis and to summarize subject accountability, demographic and baseline characteristics, and adverse event data. Subjects in this analysis set will be analyzed “as randomized”.

Per Protocol Analysis Set: All subjects who meet predetermined data usability criteria and who do not have any major protocol deviations that would necessitate exclusion from analysis. Subjects in this

analysis set will be analyzed “as treated”. This analysis set will be used as a supportive analysis of the primary endpoint.

Complete Cases Analysis Set: All subjects who have complete data for the efficacy endpoints of IOI-HA, QuickSIN, or Real Ear Measures.

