The pivotal primary endpoint analysis using the above methodology will be based on the Full Analysis Set where all randomized subjects are included in the analysis and subjects will be analyzed according to the treatment group to which they were randomized. A supportive analysis will also be performed using the Per Protocol Analysis Set where subjects will be analyzed according to the treatment received.

A Complete Cases analysis using only those subjects who have a non-missing outcome for the IOI-HA survey will also be performed using a two-sample independent non-inferiority t-test assuming equal variances. The two-sided 95% confidence interval will be reported for the (Pro-Fit – Self-Fit) mean difference. In the event there are substantial departures from the equal variances assumption, a two-sample t-test assuming unequal variances will be performed similarly.

If the non-inferiority hypothesis is rejected using the Full Analysis Set, a gatekeep strategy will be used to test for superiority to determine if the treatment effect (i.e., mean difference) is statistically different than 0 using the same two-sided significance level of 0.05. If the upper two-sided 95% confidence bound for the treatment effect (Pro-Fit – Self-Fit) is less than or equal to 0, superiority of the Self-Fit arm will also be concluded in addition to non-inferiority.

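### Could the eligibility condition in the Full Analysis Set definition drop randomised subjects from the primary analysis?

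*SAP*

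**What the plan says.** SAP Section 8 (Analysis Sets) defines the Full Analysis Set (FAS) as "All subjects who sign informed consent, meet eligibility criteria, and are enrolled and randomized into the CV portion of the study". Protocol 9.3 has the same condition: "All subjects who sign informed consent, meet eligibility criteria, and are enrolled and randomized into the study". Neither states when eligibility is judged. Both analyse the set as randomised and use it for the primary endpoint, baseline and adverse-event summaries; SAP Section 8 adds protocol deviations.

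SAP 9.5, which sets out the pivotal analysis, describes the FAS as one "where all randomized subjects are included in the analysis", each in the arm assigned by randomisation.

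Protocol 4.8 foresees late eligibility findings. One ground on which a participant may be discontinued is: "After enrollment, if a participant does not meet the inclusion/exclusion criteria of the study (either newly developed or not previously recognized". SAP 9.1 lists a matching withdrawal reason.

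On the order of entry, Protocol 4.7 states: "Following the enrollment process, participants will be randomized into either SF or PF groups". SAP 7.2 adds: "Eligible subjects will be randomized (1:1) to either the Self-Fit or the Pro-Fit groups".

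**The concern.** A full analysis set should be fixed by the act of randomisation. A definition that also requires subjects to meet the eligibility criteria, with no time point, seems to let a later finding change who is in it. Protocol 4.8 shows that such findings are expected, and several exclusions in Protocol 4.4 rest on self-report, so late discovery is plausible. Because discontinuation is optional under Protocol 4.8, such a subject could reach Clinic Visit 3 and have an IOI-HA score.

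At stake is the pivotal comparison in an open-label non-inferiority trial. If low-scoring Self-Fit subjects were removed after their scores were known, the Pro-Fit minus Self-Fit difference would shrink and non-inferiority would be easier to claim. The documents do not say who assigns subjects to analysis sets or what that person knows at the time. The adverse-event tables use the same set.

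**Working it through.** The question is one of wording, so the first step is to see whom each wording selects.

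| Subject | Literal SAP 8 / Protocol 9.3 | SAP 9.5 | Eligibility judged at entry |
|---|---|---|---|
| Eligible, never randomised | Out | Out | Out |
| Randomised, no later finding | In | In | In |
| Randomised, exclusion develops later | In, on the natural reading | In | In |
| Randomised, ineligibility present but unrecognised | Out | In | In |

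Only the last row differs. Four things in the documents bear on it.

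1. **Sequence.** The SAP 8 definition lists consent, eligibility, enrolment and randomisation in the order in which they occur. Protocol 4.10 makes meeting the criteria part of being enrolled, Protocol 4.7 places randomisation after enrolment, and SAP 7.2 randomises eligible subjects. Eligibility is therefore a gate passed on the way in.
2. **The Eligible Analysis Set.** SAP Section 8 uses the same eligibility phrase for this set and adds: "Some of these subjects may not have been randomized if the hearing loss recruitment category is already filled". Eligibility is thus a status settled before randomisation.
3. **The stated reason for leaving subjects out.** SAP Section 4 says that subjects turned away because their hearing-loss category is full "will not be included in any of the full analysis set analyses because they were not randomized". No passage gives a late eligibility finding as a reason for leaving the FAS.
4. **The planned tables.** Table 14.1.1 (Subject Accountability) is built on the Eligible Analysis Set, and SAP 9.1 includes ineligibility found after enrolment among the withdrawal reasons. On a retrospective reading, subjects withdrawn because they had never been eligible would be missing from the table meant to count them. This supports the entry-time reading but does not prove it, since the category could still hold exclusions that developed later.

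The second step is to see which subjects in the last row could affect the result. One discontinued before Clinic Visit 3 has no IOI-HA score. In the FAS, that subject is handled as missing under SAP 9.5 and adds no outcome to the mean difference. Only a subject who completes Visit 3 matters.

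The third step is scale. Inputs from the documents are n = 56 per arm (SAP 7.1) and a margin of 3 (SAP 6.3). Two inputs are assumed because the documents give neither: k, the number of scored subjects removed from one arm, and D, the points by which their average falls below those retained.

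Shift in that arm's mean = k × D / 56.

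| k | D = 2.5 | D = 5 | D = 10 |
|---|---|---|---|
| 1 | 0.04 | 0.09 | 0.18 |
| 5 | 0.22 | 0.45 | 0.89 |

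Removals from Self-Fit lower the Pro-Fit minus Self-Fit difference and removals from Pro-Fit raise it. Equal removals with the same gap cancel. With 45 scored subjects per arm (half of the 90 usable data sets in Protocol 4.2), one removal at D = 5 gives 5/45 = 0.11.

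Precision hardly moves. The 95% half-width is 1.96 × SD × √(1/56 + 1/(56 − k)). At an assumed SD of 5 it is 1.85 for k = 0, 1.86 for k = 1 and 1.90 for k = 5. At SD 4 it goes from 1.48 (k = 0) to 1.52 (k = 5), and at SD 6 from 2.22 to 2.28.

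**The case for a change.** The best case for a change is that nothing in the definition says eligibility is as judged at entry, and that the subject in question did not in fact meet the criteria at entry; this simply went unnoticed. Protocol 4.8 itself speaks of not meeting the criteria for a status discovered after enrolment, so the documents do not reserve that language for the entry decision. Read the same way, the Protocol 4.10 definition of an enrolled subject could also be undone by a later finding. Aligning the texts would take one line in each document.

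Much of this stands as a comment on drafting: the literal wordings differ, and no passage expressly covers the unrecognised case. It does not follow that the analysis is at risk. The conflict arises only if the eligibility phrase is given a retrospective force that no passage gives it, and that SAP 9.5 contradicts for the analysis that matters. The shifts above could be turned into error rates, but those would rest wholly on an assumed count, gap, SD and arm imbalance, and even the direction would be a choice. For safety, SAP 9.5 does not govern the adverse-event tables, so there the entry-time reading does the work. The adverse-event listings name no analysis set, so events in such a subject need not drop out of view.

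**Conclusion.** No change follows. This is a gap in wording that analysts fill sensibly. Followed as written, SAP 9.5 keeps every randomised subject in the primary analysis. Late eligibility findings already have a place: withdrawal reasons in SAP 9.1, deviation summaries on the FAS in SAP 9.10, and removal from the Per Protocol set when the deviation is major.

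The effect is zero if no such subject reaches Visit 3, and zero if SAP 9.5 is followed. Under the contrary reading, one removal moves an arm mean by 0.04 to 0.18 points against a margin of 3, for assumed gaps of 2.5 to 10 points. The 0.89 at the top of the table needs five scored removals, all in one arm, each group averaging 10 points below the rest; nothing in the documents points to that. The conclusion rests on taking SAP 9.5 as the governing text for the primary endpoint and on the absence of any instruction to remove randomised subjects. No bias or inflation of the error rate is shown.
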